An AE, also known as an adverse experience, is defined as any untoward medical occurrence in a patient or clinical investigation participant administered a pharmaceutical product and which does not necessarily have to have a causal relationship with this treatment (ICH GCP/Health Canada Division 5).

An AE can therefore be any unfavorable and unintended sign, symptom, abnormal results of an investigation, or disease (new or exacerbated) temporally associated with the use of the investigative product, without any judgement on causality

Events that do not meet the definition of an AE include:

- Medical or surgical procedures; the condition that leads to the procedure is an AE.
- Anticipated day-to-day fluctuations of a pre-existing disease or condition present at the start of the study that do not worsen.
- The disease/disorder being studied (eg. Recurrent urinary tract infections) or expected progression, signs or symptoms of the disease being studied, unless more severe than expected for the participant's condition.

AEs that are serious, unexpected and at least possibly related to study participation will be reported to the Research Ethics Board and to Health Canada within the timelines indicated below.

All other AEs such as those that are not serious, expected and not related to the study participation will not be reported to the local Research Ethics Board, as per local guidelines.

Serious Adverse Event Definition/ Reporting Requirements

An adverse event is considered serious if any untoward medical occurrence includes any of the following:

- a) Results in death: This includes any death that occurs while the participant is in the study.
- b) Is immediately life-threatening.
 When in the view of the Investigator, the AE places the participant at immediate risk of death. It does not include a reaction that had it occurred in a more severe form, might have caused death.
- c) Event requires in-patient hospitalization or prolongation of existing hospitalization.

In the absence of an AE, hospitalization or prolongation of hospitalization should not be reported as an SAE in the following circumstances:

- Hospitalization or prolongation of hospitalization is part of a routine procedure followed by the study centre.
- Hospitalization for survey visits or annual physicals.
- For hospitalization planned and documented before the start of the study for preexisting condition which has not worsened.
- d) Is a congenital anomaly/birth defect.

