- e) Results in persistent or significant disability or incapacity.
- f) Is an important medical event that may jeopardize the patient or may require medical intervention to prevent one of the outcomes listed above.

Recording Adverse Events

All adverse events, which include any detrimental change in the participant's condition, will be collected from the time the participant signs the consent form until the follow up period is completed at the 12 month clinic visit.

AEs will be captured wherever possible as a diagnosis and it is the Investigator's responsibility to ensure this is done. All AEs including SAEs are to be accurately recorded on the Adverse Event case report form(s). The Investigator will carefully evaluate each AE to determine severity, expectedness, relatedness and outcome as indicated below.

Severity:

- Grade 1 Mild: Participant is aware symptoms but they are easily tolerated and have no or mild impact on regular activities. Symptoms do not require medical attention or treatment.
- Grade 2 Moderate: An event the participant experiences that is of minor concern or convenience. These events may have an impact on Page 12 of 24

daily activities but can typically be improved with simple therapeutic measures. These experiences may interfere with the participant's normal functioning.

- Grade 3 Severe: These events are usually incapacitating to the participant. They impact normal daily activities and typically require treatment or systemic drug therapies.
- Grade 4: Life threatening or disabling.
- Grade 5: Death

Expectedness

AEs must be classified based on whether or not they were expected given current knowledge of the study treatment and procedures:

- Unexpected: The event is not expected based on current information of the condition or the study treatment as outlined in the protocol, investigator's brochure or consent form. Is considered for expedited reporting purposes when the type or event or severity of the event is not listed in the current IB.
- *Expected:* The event is known to be associated with the condition being studied or the intervention.

Expected AES

Expected transient AEs associated with treatment reported occurrence <10%.

- Post nasal drip
- Stinging around mouth
- Pruritus over old BCG scar
- Pruritus over abdomen
- Intermittent abdominal pain
- Mild nausea
- Asthma exacerbation

Serious Adverse Event

Reported occurrence <2%.

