The Principle Investigator provides oversight of the study with assistance from the research coordinator. One of the purported advantages of sublingual administration is greater safety, which allows for administration of this treatment outside of the medical setting.

First dose will occur in medical setting and research coordinator will monitor and record any adverse reactions. Participants will be provided with specific instructions as to how to administer treatment at home and advised to call the research coordinator if bothersome adverse events are experienced. If a dose is missed the participant is not to make up missed dose but resume next scheduled dose. Additionally, the research coordinator will follow-up with each participant within one week of start of treatment to assess any adverse reactions.

The PI will review all study data and any adverse events in real time and reports all SAEs to the study monitor, study safety lead, research ethics board as per local guidelines. AEs are assessed at each study visit by the study team or during review of hospital chart at hospital admission.

All AEs will be assessed and therapeutic strategies implemented according to medical opinion of the PI. Additionally, SAEs will be assessed by the study safety lead.

Occurrence of a UTI

Should a study participant experience a UTI throughout the course of the trial, it will not be captured as an AE. The UTI, along with the symptoms, medical attention and treatment received will be captured through the participant's diary and recorded in the electronic data capture system.

The Investigator must submit sufficient initial information to Health Canada should the SAE report meet the criteria (serious, unexpected and possibly or related to study treatment) for completion of an Adverse Event Drug Reaction Expedited Reporting Summary form and CIOMS report.

As much of the following information about the participant and the event will be requested:

- Participant study code, gender, age, or date of birth
- Underlying diagnosis and extent of disease
- Lot number and expiration date of study drug
- Date of last study drug administration
- Date of death (if applicable)
- Intervention required
- Concomitant medications
- Pertinent laboratory data
- Pertinent medical history
- Study drug status (dose interrupted, discontinued)

- Did event abate after interruption of study drug administration (if applicable)
- Did event recur after study drug was reintroduced (if applicable)

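### The protocol's expectedness tests conflict, so a serious, possibly related disease-type event not listed in the Investigator's Brochure can be classed as expected and not expedited

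*Combined protocol and SAP*

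**What the plan says.** Four statements under Recording Adverse Events, Expectedness, bear on the point.

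- The lead-in: "AEs must be classified based on whether or not they were expected given current knowledge of the study treatment and procedures". The disease is not named.
- The first sentence of *Unexpected*: "The event is not expected based on current information of the condition or the study treatment". It accepts the protocol, the IB or the consent form as the source.
- The second sentence of *Unexpected*: "Is considered for expedited reporting purposes when the type or event or severity of the event is not listed in the current IB". This is the only one of the four that mentions expediting.
- *Expected*: "The event is known to be associated with the condition being studied or the intervention". It refers neither to the IB nor to severity.

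Two places turn the classification into a reporting duty. Adverse Event (AE) states: "AEs that are serious, unexpected and at least possibly related to study participation will be reported to the Research Ethics Board and to Health Canada". Under Occurrence of a UTI, the expedited summary form and CIOMS report are due "should the SAE report meet the criteria (serious, unexpected and possibly or related to study treatment"). Governing Regulatory Authorities sets the clock: 7 calendar days for fatal or life-threatening events, 15 for the others.

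Two further statements limit which events get this far. Adverse Event (AE) leaves out the disease and its expected course unless the event is worse than expected for that participant. Occurrence of a UTI says that UTIs during the trial are not recorded as adverse events.

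**The concern.** Whether Health Canada receives a case report depends on one word, *unexpected*, and the section that defines it does so in incompatible ways. Events that resemble the disease are the ones affected, and for a vaccine against urinary infection they are a plausible place for harm to appear, for example as an unusually severe infection.

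Three features of the trial make the classification matter more than usual. Ordinary UTIs are kept out of adverse event reporting, so severe disease-type events are what remains of an infection signal there. There is no concurrent control arm in which an excess could be seen. And the investigator, who classifies the event, also carries the sponsor's reporting duty, so there is no separate sponsor to correct a classification made under the wrong bullet.

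**Working it through.** No sample size, rate or power figure is involved, so the check is to pass one case through each statement.

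**Test case.** An event that is (a) serious, (b) judged possibly related to Uromune, (c) known to be associated with recurrent UTI, (d) more severe than expected for the participant, so that it still counts as an adverse event, and (e) not listed in the IB. A serious kidney or bloodstream infection can serve as an illustration. That such an infection meets (c) and (e) is an assumption, and the IB is not among the documents.

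| Statement under Expectedness | What it looks at | Class of the test case |
|---|---|---|
| Lead-in | Treatment and procedures | Unexpected, if not otherwise known for Uromune |
| *Unexpected*, first sentence | Condition or treatment, as described in protocol, IB or consent form | Not unexpected if one of these documents ties it to the condition |
| *Unexpected*, second sentence | Type and severity against the IB, for expediting | Unexpected |
| *Expected* | Known association with condition or intervention | Expected |

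**Applying the triggers.** Both require serious, unexpected and at least possibly related. The first and third conditions are met by construction.

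- With the IB sentence, the second condition is met and the report is due in 7 or 15 days.
- With the *Expected* bullet, the second condition fails and no expedited report is due, although the event has been judged possibly related.

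Neither trigger points to one test, and no order of precedence is written down.

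**What the rest of the protocol implies.** The section on SAE review and potential impact on the trial speaks of lists of expected suspected reactions, to be extended when events are newly identified as drug-related. That treats expectedness as a list of drug reactions. The same section already has the investigator weigh the underlying condition when judging causality. Weighing it again under expectedness lets an event that passed the causality judgement drop out at the next step.

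**Other routes for the same case.**

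- All SAEs go to the investigator, monitor and safety lead within 24 hours (SAE review section). This is internal.
- SAEs go to the ethics board as local guidelines require (Risk Mitigation). This is not the regulator.
- Health Canada must be notified of a new drug-related event that raises a safety concern (SAE review section). This does not depend on expectedness, but it needs a related event and a judgement of concern, and it carries no 7- or 15-day limit.
- Adverse events are reviewed in aggregate each month (Study Monitoring).
- The stopping rule does not depend on expectedness, but it needs more than 20% of participants with treatment-emergent SAEs. With 80 enrolled that is more than 0.20 × 80 = 16, so a few cases would not reach it.

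**The case against.** The strongest reply is that only one sentence addresses expediting, and it names the IB. A specific rule normally governs over a general one, the lead-in points the same way, and Governing Regulatory Authorities places expedited reporting under Health Canada Division 5 and ICH guidance. On that reading the test case is reported and the *Expected* bullet serves only for classification on the case report form. This is a fair reading, and it makes the failure possible rather than built in. It does not remove the conflict. The protocol states no such precedence, the IB sentence has no grammatical subject, and both triggers say only that the event must be unexpected.

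A second reply is that an event already judged worse than expected for the participant can hardly be called expected. That has force in practice, but the *Expected* bullet has no severity qualifier that would compel this answer.

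A reader might infer that no disease-type event could ever be expedited, or that every such event moves from mandatory reporting to none. The documents do not support that. The outcome depends on which sentence is applied, and Health Canada can also be reached through the safety-concern duty. Nor would such events be hidden, since the 24-hour reports, ethics board reporting, safety-lead assessment and monthly review all stand.

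A reader might also infer that the IB lists no infections, because the protocol's own list has seven transient events and one rash and nothing infectious or urinary. That list cannot show what the IB contains.

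**Conclusion.** The conflict is real and can change whether a regulatory report is made. It affects a narrow class: serious, possibly related events that are known to go with the condition, are severe enough to count as adverse events, and are not in the IB. For these, adjacent bullets give opposite answers, and the 7- or 15-day report depends on the choice. The existing safeguards reduce the risk but do not substitute for that report.

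The size is one report per affected case. No frequency can be derived from the documents. The conclusion does not depend on the content of the IB, except that an event listed there with matching severity would be expected under the IB sentence too. Ordinary UTIs, and disease-type events no worse than expected, never reach the expectedness step and are not part of this point. This is an inconsistency of wording to be corrected. It does not affect the efficacy analysis.

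**What to change.** Reconcile the sections so that one test governs:

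- Under Expectedness, state that for expedited reporting an event is expected only if its type and severity are listed for Uromune in the current IB.
- Add a cross-reference to that rule at both triggers, under Adverse Event (AE) and Occurrence of a UTI.
- For that purpose, remove the condition under study from the *Expected* bullet and the condition from the first sentence of *Unexpected*. Association with the disease is then weighed once, under Relatedness.

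Nothing wider is needed. The protocol's own list of expected events and the consent form can stay as general references, provided the text says that the IB decides for expediting.

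The cost is a few lines of protocol wording and possibly a few more expedited reports. Treatment, visits and analyses are unchanged. The change does not bring ordinary UTIs into adverse event capture.

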• Severe rash face and neck within 2 days of start of treatment and after restarting the treatment several times a month later. No evidence of airway compromise or anaphylaxis reaction. Antihistamines given to relieve symptoms.

Relatedness

The Investigator must attempt to determine if an AE or SAE is related to the use of the study treatment or procedures:

- **Related:** The adverse event is clearly related to the procedures or the study treatment.
- **Possibly Related**: An adverse event that follows study treatment administration. The event follows a known or expected response but could have been produced by other factors.
- **Not Related**: The adverse event is clearly not related to the procedures or investigational product.

Outcome of an SAE

Each SAE will need to be followed for outcome. The outcome of each SAE will need to be reported on throughout the duration of the study. Each SAE can be reported as:

- Resolved
- Recovered with minor sequelae
- Recovered with major sequelae
- Ongoing/Continuing treatment
- Condition worsening
- Death
- Unknown

This information will be collected on the AE Log case report form.

Follow-up of Unresolved Adverse Events

During the course of the study, all AEs and SAEs will be proactively followed up for each participant for as long as the event is ongoing. Every effort will be made to obtain a resolution for all events, even if the events continue after the participant has discontinued study drug or the study has completed.

Any AEs that are unresolved at the participant's last visit in the study are followed up by the Investigator for as long as medically indicated, but without further recording in the case report form. The Investigator of this study, [name] retains the right to request additional information for any participant with ongoing AEs or SAEs at the end of the study, if judged necessary.

Serious Adverse Event and Serious and Unexpected Suspected Adverse Reaction Review and Potential Impact on Trial

The investigator will review each SAE report and evaluate the relationship of the SAE to the study drug and to the participant's underlying condition.

Based on the Investigator's assessment of causality of the AE and discussions with the Safety Lead, a decision will be made by the Investigator concerning the need for further action with respect to the future conduct of the study. The primary consideration governing action is whether new findings affect the safety

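### Read literally, the Possibly Related definition leaves a serious event of a new type and uncertain cause without a causality class, so it misses the Health Canada reporting criterion

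*Combined protocol and SAP*

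**What the plan says.** The protocol's *Relatedness* section gives three classes and no others:

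- Related: "The adverse event is clearly related to the procedures or the study treatment".
- Possibly Related, in two sentences: "An adverse event that follows study treatment administration", followed by "The event follows a known or expected response but could have been produced by other factors".
- The last class, Not Related, again needs a firm judgement: "The adverse event is clearly not related to the procedures or investigational product".

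There is no unassessable class and no default for uncertain cases.

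*Expectedness* is a separate judgement. An event is unexpected when "The event is not expected based on current information of the condition or the study treatment" applies, judged against the protocol, investigator's brochure or consent form. For expedited reporting, the section adds that an event also counts as unexpected if its type or its severity is missing from the current brochure.

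The reporting criterion appears twice. *Adverse Event (AE)* sets it for both Health Canada and the ethics board: "AEs that are serious, unexpected and at least possibly related to study participation will be reported". The Health Canada paragraph placed under *Occurrence of a UTI* repeats the test as "serious, unexpected and possibly or related to study treatment".

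**The concern.** Expedited reporting serves to pass on serious reactions that are new and whose cause is still open. The protocol's only class for an open cause is tied to a response that is already known. Causality and expectedness, which the protocol asks the investigator to judge separately, are thereby mixed inside one definition.

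At stake is whether such an event reaches Health Canada under the protocol's own rule. The investigator also holds the sponsor role for that reporting (*Governing Regulatory Authorities*). The protocol describes no separate sponsor causality review with a different definition that would catch the event.

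**Working it through.** No arithmetic applies. The check takes the definitions literally, crosses causality with expectedness for a serious event after dosing, and asks which class each case falls in and whether the Health Canada criterion (serious, unexpected, and possibly related or related) is met.

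| Case | Type and severity | Cause | Class available | Criterion met? |
|---|---|---|---|---|
| a | New type | Clearly related | Related | Yes |
| b | New type | Clearly not related | Not Related | No, properly |
| c | New type | Uncertain | None | No |
| d | Known type, unlisted severity | Uncertain | Possibly Related | Yes |
| e | Known type, listed severity | Uncertain | Possibly Related | No, because expected |

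Case c, step by step:

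1. The relation is not clear, so Related fails.
2. The absence of a relation is not clear, so Not Related fails.
3. The event follows dosing, so the first sentence of Possibly Related is met. The type is new, so the second sentence is not.
4. No class remains. The event is not at least possibly related, and the criterion is not met.

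For new event types, therefore, the written rule reaches only clearly related events (case a).

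Next, does any other provision bring case c to Health Canada?

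| Provision | Who is told | Reaches Health Canada in case c? |
|---|---|---|
| *Safety Reporting*: all AEs, under local guidelines | Ethics board | No |
| SAE review section (*Potential Impact on Trial*): all SAEs within 24 hours, whatever the causality | Investigator, monitor, safety lead | No |
| Same section: immediate notice on a safety concern | Health Canada | No; it applies to a new AE already judged related |
| *Risk Mitigation*: all SAEs, under local guidelines for the ethics board; the safety lead also assesses SAEs | Monitor, safety lead, ethics board | No |
| *Study Monitoring*: monthly aggregate AE review | Monitor, investigator, safety lead | No |
| *Ethical Considerations*: unexpected issues involving risk, with no causality condition | Ethics board | No |

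Two further observations follow:

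- The ethics-board statements do not agree. *Adverse Event (AE)* limits ethics-board reporting to serious, unexpected and at least possibly related events. *Safety Reporting*, *Risk Mitigation* and *Ethical Considerations* are each wider.
- Possibly Related requires the event to follow study treatment. Yet AEs are collected from consent (*Recording Adverse Events*), the criterion in *Adverse Event (AE)* refers to study participation, and both clear classes mention procedures. An event of uncertain cause that follows a study procedure before the first dose also has no class.

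**The case against.** The strongest reply is that the protocol should be read as a whole. It asks for expectedness and relatedness separately. Its reporting criterion presupposes that an event can be both unexpected and possibly related, and one section heading names serious and unexpected suspected reactions. A sensible investigator would treat timing as enough and choose Possibly Related. *Governing Regulatory Authorities* also places expedited reporting under named Health Canada and ICH guidance.

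The point about intent stands: this is a drafting inconsistency, not a decision to exclude such events. It does not remove the gap, because the sensible choice means setting aside the second sentence of the definition. The content of the external guidance is not in the documents and cannot be relied on here.

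A reader might infer more than the text supports:

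- *That every unexpected serious event of uncertain cause is lost.* It is not. An event unexpected only by severity can follow a known response and remains reportable (case d).
- *That such events escape reporting altogether.* They do not. The 24-hour internal route applies whatever the causality, and ethics-board routes exist.
- *That the trial's safety analysis or stopping decision is distorted.* No tabulation by causality is planned in *Analysis*. The stopping rule counts treatment-emergent serious events without a relatedness condition.
- *That the small earlier experience (75 evaluable women in the UK series, 136 vaccine recipients in the Spanish study) shows most unlisted events would be affected.* Whether an event is unexpected follows from the definition and the brochure listing, not from those sample sizes, and the brochure is not part of the documents.

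**Conclusion.** The point holds in a narrow form. On a literal reading, a serious event that is unexpected by type and of uncertain cause has no causality class and does not meet the criterion for reporting to Health Canada, and no other provision sends it there.

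In size, this is one cell of the cross-classification (case c). How many of the planned 80 participants might have such an event cannot be estimated from the documents.

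The conclusion assumes that a known or expected response is judged against the same current information that defines expectedness, and that the second sentence of Possibly Related is a condition rather than an illustration. If investigators ignore that sentence, the event is reported, but then reporting depends on departing from the text. The matter is worth correcting because it sits in the trigger for regulatory safety reporting and the correction is small.

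**What to change.** In *Relatedness*, remove the known-response condition and redefine the middle class along these lines:

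> Possibly Related: an event that follows study treatment or a study procedure, for which a causal relationship is a reasonable possibility whether or not the response is already known, and which other factors could also have produced. Any event that is neither clearly related nor clearly unrelated is assigned to this class.

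Keep *Expectedness* as a separate judgement. The Health Canada criterion itself can stay as written in *Adverse Event (AE)* and under *Occurrence of a UTI*. Reconcile the ethics-board statements in *Safety Reporting*, *Adverse Event (AE)*, *Risk Mitigation* and *Ethical Considerations* so that one rule applies.

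The cost is one definition, the matching CRF completion instructions, and an edit to the ethics-board statements. The downside is that some more events may be classed as possibly related; the documents give no basis for a number. Endpoints, sample size and the stopping rule are untouched.
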